#### 3.3.7 Data analysis

Odds ratios for different risk factors for CDI will be compared between settings (community/hospital) and countries. Risk factor comparison will also be made between different strain types (as identified in O1.2).

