## 2.1 Selection of case and controls (total possible to be recruited)

		Location	of participant a sample	at time of
Diagnostic categories:		Hospital	Community	TOTAL
CDI positive cases	1. CCNA positive	83	20	103
	2. CCNA negative/Simoa positive	49	22	71
	3. CCNA and Simoa negative but CTC positive or bioFire pos	24	15	39
CDI negative controls	4. Negative control *	365	147	512
Total number selected for case/control study 521 204		725		

Table1. The total number of samples selected for the case/control study (n=725). The table shows the number of CDI positive cases according to the indicated diagnostic categories (1-3, n=213) and by location of participant (Hospital n=156, Community n=57). Negative controls (4, n=512) were selected at a rate of 1:3 from matching participating sites (one case to three controls). As some participating sites had less than 3 controls per case, average rate was of 1:2.4 (one case to 2.4 controls) (\*).

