#### 2.5. Analysis objectives

The main objectives of the analyses are to;

- 1. Determine the outcomes of cases (of each classification) vs controls, and compare between countries and hospital vs community cases
- 2. Determine the risk factors for cases (of each classification) vs controls, and compare between countries and hospital vs community cases

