#### 3. Sample size

Based on a previous risk factor study using a similar study design (ORCHID) the following power calculations were made;

Age >65; previously found 65% in cases and 39% in controls. Comparing proportions for equivalence, a sample size of 20 cases and 60 controls would give 80% power to detect a difference of 23% between cases and controls with an  $\alpha$  type one error rate of 5%.

At least one antibiotic; previously found 67% in cases and 45% in controls. Comparing proportions for equivalence, a sample size of 23 cases and 67 controls would give and 80% to detect a difference of 22% between cases and controls with an  $\alpha$  type one error rate of 5%.

At least one antibiotic; alternative single centre cohort found 85% in cases and 75% in controls. Comparing proportions for equivalence, a sample size of 92 cases and 276 controls would give and 80% to detect a difference of 13% between cases and controls with an  $\alpha$  type one error rate of 5%.

Previous surgery; previously found 26% in cases and 16% in controls. Comparing proportions for equivalence, a sample size of 156 cases and 469 controls would give and 80% to detect a difference of 10% between cases and controls with an  $\alpha$  type one error rate of 5%.

Previous surgery; alternative single centre cohort previously found 41% in cases and 28% in controls. Comparing proportions for equivalence, a sample size of 88 cases and 351controls would give and 80% to detect a difference of 13% between cases and controls with an  $\alpha$  type one error rate of 5%.

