#### 4. Study Design

This is case-control study with the cases and controls selected from the patients who had stool samples tested for CDI. The study will collect data on cases/controls (1:3 ratio) identified during the sample collection phase of COMBACTE-CDI.

For each case of confirmed CDI (or other diagnostic criteria), three controls will be randomly selected from the same participating site (i.e. if hospital case, controls will come from the same hospital, if community case, controls will come from the community). Thus initially the controls are only matched on location only, as the cohort is not large enough to enable closer matching. Subsequent further matching (e.g. by age) may be considered depending on final available sample size, but this would reduce the overall pool of controls substantially.

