#### 4.2 Analysis sets and subgroups

Data will be analysed to determine the outcomes and possible risk factors for CDI based on the different diagnostic criteria. Comparisons will be made between outcomes and risks for different countries and healthcare settings (hospital, community). Sample size will be too small to perform subgroup analysis within each country.

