#### 7.2 Univariate analysis

Univariate analysis will be used to assess outcomes and risk factors; continuous variables will be compared between cases and controls by t-test; categorical variables will be compared between cases and controls by chi-squared (fishers exact where numbers are below 5). Risk ratios (Odds ratio if it is case control study) will be calculated for CDI cases with identified variables of interest. Univariate analysis will be used to assess consistency between countries and between different healthcare settings.

The variables to be included in the univariate analysis are shown in the table in appendix 1.

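### The SAP promises to compare risk factors between hospital and community, but no named analysis estimates or tests whether an odds ratio differs between the two settings

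*SAP*

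**What the plan says.** Both main objectives in SAP 2.5, for outcomes and for risk factors, end by promising to "compare between countries and hospital vs community cases". SAP 4.2 repeats this: "Comparisons will be made between outcomes and risks for different countries and healthcare settings (hospital, community"). Protocol 3.3.7 says: "Odds ratios for different risk factors for CDI will be compared between settings", and between countries, without naming a method.

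The method is in SAP 7.2: "Univariate analysis will be used to assess consistency between countries and between different healthcare settings". The tests named in that section are a t-test for continuous variables and, for categorical ones, "categorical variables will be compared between cases and controls by chi-squared", with Fisher's exact test for small numbers. Odds ratios are calculated, but nothing says how they are to be compared across settings or what would count as inconsistent.

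SAP 7.3 plans a logistic model with forward selection, run separately by age group. It names no product term with setting or country. Location is item 1.4 in SAP Appendix 1, so it can enter as a main effect; country is not in that table.

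SAP Table 1 gives the cases "by location of participant (Hospital n=156, Community n=57") and 365 and 147 controls. Controls follow the setting of their case: "if hospital case, controls will come from the same hospital, if community case, controls will come from the community".

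**The concern.** Whether a risk factor acts differently in hospital and in the community is a question about the difference between two odds ratios. A case-control test within each setting does not answer it. Nor does location as a main effect: controls were selected by location, so that coefficient largely reflects the sampling ratio (365/156 = 2.34 in hospital, 147/57 = 2.58 in the community).

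With no stated rule, the natural fallback is to see which exposures reach significance in each setting. Hospital has almost three times as many cases (156/57 = 2.7), so the same effect would often be significant there and not in the community. A difference in precision could then be published as a hospital-only risk factor. The choice of rule would also be made after seeing the data, across the many variables in Appendix 1.

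**Working it through.** **Text check.** SAP 2.5, 4.2, 7.1-7.3 and Appendix 1, and protocol 3.2.7 and 3.3.7, contain no interaction term, heterogeneity test or ratio of odds ratios. SAP 3 gives sample sizes for case-control differences only, so the documents hold no figure for this comparison to reproduce.

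**Inputs.** Counts are from SAP Table 1: hospital cases 83 + 49 + 24 = 156, community cases 20 + 22 + 15 = 57, controls 365 + 147 = 512. Exposure rates are from SAP 3, for example "Age >65; previously found 65% in cases and 39% in controls". Assumptions: two-sided 5%, the three case categories pooled, all forms returned, and the same exposure rates in both settings.

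**Step 1: separate tests under one common effect.** If the power is P_H in hospital and P_C in the community, the chance that exactly one is significant is P_H(1 - P_C) + (1 - P_H)P_C. For surgery 26/16, P_H = 0.746 and P_C = 0.383. This gives 0.746 x 0.617 + 0.254 x 0.383 = 0.460 + 0.097 = 0.557, of which 0.460 is hospital only. Simulation with 200,000 runs per scenario gives:

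| SAP 3 scenario (cases/controls, %) | OR | Exactly one setting significant | False signal, interaction test |
|---|---|---|---|
| Age >65 (65/39) | 2.90 | 8% | 4.9% |
| Antibiotic (67/45) | 2.48 | 18% | 4.8% |
| Antibiotic, alternative cohort (85/75) | 1.89 | 58% | 4.4% |
| Surgery (26/16) | 1.84 | 56% | 4.7% |
| Surgery, alternative cohort (41/28) | 1.79 | 54% | 4.8% |

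For the three smaller effects, the split is 46-49% hospital only and 8-10% community only. The interaction test is a Wald test of the difference in log odds ratios, with 0.5 added to each cell. A logistic model with country, setting and exposure, tested by likelihood ratio, gave 5.0-6.0% false signals (3,000 runs each; country counts are not given, so they were assumed equal or proportional to planned sites).

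**Step 2: precision of the ratio of odds ratios.** Within a setting, var(log OR) = 1/[n1 p1(1 - p1)] + 1/[n0 p0(1 - p0)], where n1 and p1 refer to cases and n0 and p0 to controls. For age >65:
- hospital: 1/(156 x 0.2275) + 1/(365 x 0.2379) = 0.0397
- community: 1/(57 x 0.2275) + 1/(147 x 0.2379) = 0.1057
- SE of the log ratio = sqrt(0.0397 + 0.1057) = 0.38
- ratio detectable with 80% power = exp(2.80 x 0.38) = 2.9

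In table order the SEs are 0.38, 0.38, 0.49, 0.44 and 0.38, and the detectable ratios 2.9, 2.9, 3.9, 3.5 and 2.9. The 95% interval multiplies and divides the estimate by 2.1 to 2.6.

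**Step 3: power at the plan's own effects.** The SAP 3 odds ratio is placed in one setting and 1.0 in the other, both ways round. Power is 80-81% (age >65), 67-69% (antibiotic), 24-31% (antibiotic, alternative), 22-27% (surgery) and 29-32% (surgery, alternative).

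**Step 4: sensitivity.** With community control exposure at half or three-quarters of the SAP 3 value, discordance in table order becomes 8-12%, 18-22%, 49-51%, 58-62% and 57-61%. The pattern holds, but the point figures are not firm.

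**The case against.** The strongest objection is that the harm rests on a procedure the SAP does not describe. A reader might infer that SAP 7.2 plans to compare separate p-values. The text does not support that: odds ratios are calculated, and protocol 3.3.7 says that odds ratios will be compared. This stands, so the discordance figures are conditional. What remains is that no way of comparing the odds ratios is given, and the only tests named do not do it.

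A reader might also extend the criticism to the 12 countries. The documents do not support the same weight there. SAP 4.2 already says the sample is too small for subgroup analysis within each country, and country counts are not given, so any country figure rests on assumption.

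Third, an interaction test does not answer the whole objective. SAP 2.5 asks for each case classification and for outcomes as well. Pooling the three case categories covers only risk factors by setting. Within a category, even an odds ratio of 2.5 in one setting and 1.0 in the other gives power of only 7-39% (category 1), 10-37% (category 2) and 4-24% (category 3). This stands.

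Fourth, the three effects for which separate tests mislead most are those for which the interaction test would usually miss a real difference (22-32% power). This also stands. It is a reason to report the ratio with its interval and to draw cautious conclusions; it does not make separate case-control tests an answer to the question.

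Finally, Table 1 shows the total possible to recruit, and SAP 4.1.5 removes some controls after form receipt, so power is a ceiling. For an odds ratio of 2.5 against 1.0 it is 42-70% over the SAP 3 control exposures with full return, and would fall to about 33-60% at 80% return and 22-48% at 60% (assumed rates).

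**Conclusion.** The point holds for the comparison of risk factors between hospital and community. It is a stated objective without a matching analysis; the overall case-control estimates are not affected. If separate p-values were read side by side, a common effect would look setting-specific in about 8% of studies for age over 65, 18% for antibiotics and 54-58% for the three smaller SAP 3 effects, against about 4-5% for an interaction test. These figures assume the full Table 1 counts, pooled case categories and equal exposure rates in the two settings. They show what an unspecified rule could lead to; they do not describe what the SAP says will be done. Because each setting has its own controls, the interaction can be estimated from data already planned.

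**What to change.** In SAP 7.2, state that for age over 65, at least one antibiotic and previous surgery, consistency between settings will be judged from the odds ratio in each setting and the ratio of odds ratios with its 95% interval, and not from separate p-values. These come from an exposure-by-setting term in a logistic model with setting and country, all case categories pooled. Country is preferable to site as a term: 119 sites among at most 725 patients would be sparse.

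Label the analysis exploratory. Present results by case classification, by country and for outcomes as descriptive estimates with intervals. State that a non-significant interaction is inconclusive and will not be reported as consistency.

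The cost is some SAP wording, country added to the variables used, and one model term per exposure; no new data are needed. The price in interpretation is low power, with only ratios of about 2.9-3.9 detectable at 80%. Three tests at 5% also carry a chance of 1 - 0.95^3 = 14% of at least one false interaction if they are independent.

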#### 7.3 Regression analysis (or Multivariate analysis)

To evaluate risk factors considering confounding, unconditional logistic regression analysis will be perform with case/control as dependent variable, and all variables listed in the univariate analysis as independent variables.

To build the logistic regression model, we will apply a stepwise forward selection to identity risk factors. The process of the forward selection will be recorded to rank the risk factor.

The regression analysis will be performed separately for the three age groups (18-49,50-64 and 65+ years). If there is a reasonable sample size analysis will also be performed for the age group <18 years.

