2.7	Did the patient receive any supportive measures/domestic help by friends or relatives during the presence of CDI?	Binary	Univariate/multivariate	Patient admission when the sample was taken

2.7.1	If yes, how many hours per day?	Continuous	Univariate/multivariate	Patient admission when the sample
				was taken
2.8	Did the patient receive any supportive measures/domestic help by professionals during the presence of CDI?	Binary	Univariate/multivariate	Patient admission when the sample was taken
2.8.1	If yes, how many hours per day?	Continuous	Univariate/multivariate	Patient admission when the sample was taken
2.9	Were any CDI related purchases necessary?	Binary	Univariate/multivariate	Patient admission when the sample was taken
2.9.1	If yes, please describe below	Categorical	Univariate/multivariate	Patient admission when the sample was taken
3. Laborat	ory Testing	1	1	
3.1	Did the patient have any test for other enteric pathogens up to 7 days before or up to 7 days after the EUCLID sample was taken	Binary	Univariate/multivariate	Patient admission when the sample was taken
3.1.1	If yes please indicate test results	Categorical	Univariate/multivariate	Patient admission when the sample was taken
3.2	What was the local policy for repeat testing of patients with CDI (at the time of the sample)	Binary (repeat or not repeat)	Univariate/multivariate	Patient admission when the sample was taken
4. CDI Test	ting	ſ	ſ	
4.1	Was the patient tested for CDI due to diarrhoea in the 6 months before the index sample	Binary	Univariate	Up to 6 months previous to the sample
4.1.1	If yes, date of sample and result of tests	Number of days between sample and	Univariate	Up to 6 months previous to the sample

		test is		
		Continuous		
		Decult of		
		Result of		
		Catagorical		
12	Did the nationt	Rinary	Univariato	Up to 6 months
4.2	have a diarrhoea	binary	Univariate	after the sample
	enisode in the 6			arter the sumple
	months following			
	the index sample			
4.3	Was the patient	Binary	Univariate	Up to 6 months
	tested for CDI in the	,		after the sample
	6 months following			
	the index sample			
4.3.1	If yes, date of	Number of	Univariate	Up to 6 months
	sample and result	days		after the sample
	of tests	between		
		sample and		
		test is		
		Continuous		
		Result of		
		test is		
		Categorical		
4.4	Was the Clostridium	Binary	Univariate	Patient admission
	difficile sent for	,		when the sample
	ribotyping?			was taken
4.5	Was the severity of	Binary	Univariate	Patient admission

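### Controls are matched to cases on site and setting, but the planned analysis ignores site, so odds ratios for exposures that vary between sites are attenuated or confounded

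*SAP*

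**What the plan says.** **Design.** SAP section 4 says that for each case "three controls will be randomly selected from the same participating site (i.e. if hospital case, controls will come from the same hospital", with community controls for community cases. It describes the controls as matched on location and on nothing else. The note to Table 1 (SAP 2.1) records uneven supply: "As some participating sites had less than 3 controls per case, average rate was of 1:2.4". SAP 4.1.5 also expects the ratio to vary with site sample size.

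**Analysis.** SAP 7.2 plans t-tests, chi-squared or Fisher tests and odds ratios, all unstratified. It adds "Univariate analysis will be used to assess consistency between countries and between different healthcare settings", which looks for heterogeneity but does not adjust for matching. SAP 7.3 says "To evaluate risk factors considering confounding, unconditional logistic regression analysis will be perform", with forward selection whose order is used to rank risk factors. "The regression analysis will be performed separately for the three age groups (18-49,50-64 and 65+ years".

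**Variables.** Appendix 1 lists patient location (item 1.4) as a candidate, but does not force it into any model. It lists no site, country or matched-set variable. It also offers as a univariate and multivariate candidate "What was the local policy for repeat testing of patients with CDI (at the time of the sample" (item 3.2), which describes the site and not the patient.

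**The concern.** Matching makes the controls resemble the cases on everything that clusters by site. If site is then left out of the analysis, two things can happen:

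- **Attenuation.** The pooled odds ratio averages over sites with different exposure prevalence and moves toward 1. A null exposure is unaffected by this route.
- **Confounding by control supply.** If sites short of controls have systematically higher or lower exposure, the pooled controls are weighted differently from the pooled cases. The odds ratio can then move either way, even when the true value is 1.

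An exposure with the same prevalence at every site suffers neither. Antibiotic use is a plausible example of one that does vary.

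Risk factors are one of the two main analysis objectives (SAP 2.5; protocol objective 1.4), and the forward-selection order is itself a reported result. Exposures that cluster by site could therefore be understated or misplaced in the ranking. Estimates made within one setting or country are less exposed, because part of the between-site variation drops out.

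**Working it through.** **1. The plan's ratio.** From Table 1, 512/213 = 2.40, so 1:2.4 reproduces. A full 1:3 would need 3 × 213 = 639 controls, so the shortfall is 127. By setting, the ratio is 365/156 = 2.34 in hospital and 147/57 = 2.58 in the community.

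**2. Setting after matching.** Hospital patients are 156/213 = 73.2% of cases and 365/512 = 71.3% of controls (chi-squared p = 0.59). The odds ratio, (156 × 147)/(57 × 365) = 1.10, is simply 2.58/2.34, the ratio of control supplies. It says nothing about risk. Forward selection would probably not pick location on this marginal association.

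**3. Illustration from SAP section 3.** For antibiotics, one cohort "previously found 67% in cases and 45% in controls", while an "alternative single centre cohort found 85% in cases and 75% in controls". Treat these as two sites with 100 cases each. For true effects, exposed cases total 67 + 85 = 152 and unexposed 48. For no effect, cases take the control prevalence: 45 + 75 = 120 exposed and 80 unexposed.

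Crude OR = (exposed cases × unexposed controls)/(unexposed cases × exposed controls). Mantel-Haenszel OR = Σ(ad/T)/Σ(bc/T) over sites.

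| Control ratio at the 45% site, 75% site | Crude OR | Mantel-Haenszel OR |
|---|---|---|
| 3.0, 3.0 | (152 × 240)/(48 × 360) = 2.11 | 43.58/19.58 = 2.23 |
| 3.0, 1.8 | (152 × 210)/(48 × 270) = 2.46 | 41.30/18.37 = 2.25 |
| 1.8, 3.0 | (152 × 174)/(48 × 306) = 1.80 | 39.63/17.98 = 2.20 |
| 3.0, 1.8, no effect | (120 × 210)/(80 × 270) = 1.17 | 1.00 |
| 1.8, 3.0, no effect | (120 × 174)/(80 × 306) = 0.85 | 1.00 |

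The unequal ratios average 2.4, as achieved. For previous surgery (26/16% and 41/28%) at an equal ratio, the crude OR is 1.79 and Mantel-Haenszel 1.81.

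The gaps between the control prevalences are logit(0.75) − logit(0.45) = 1.30 and logit(0.28) − logit(0.16) = 0.71. Read as two draws (gap/√2), they suggest SDs of about 0.9 and 0.5. This is indicative only.

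**4. Simulation.** From the documents: 156 hospital and 57 community cases, mean ratio about 2.4, control exposure 45%. Assumed: 60 or 119 contributing sites, skewed case loads, about 40% of sites short of controls, and the between-site SDs. The model is all-age with setting included; the true OR is 2.0; there were 300 replicates per scenario.

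| Between-site logit SD | Unconditional OR, supply unrelated to exposure | 95% CI coverage |
|---|---|---|
| 0.5 | 1.92–1.95 | 95–96% |
| 0.9 | 1.79–1.80 | 91–92% |
| 1.5 | 1.65 | 79–82% |

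Conditional on site by setting, the OR was 1.98–2.03. With an assumed supply–exposure correlation of +0.5 the unconditional OR was 1.40–1.82, and with −0.5 it was 1.89–2.07. With a true OR of 1.0 it was 1.00 at zero correlation and 0.85–1.18 at ±0.5.

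**5. A second calculation under different assumptions** (119 sites, half at 1:3 and half at 1:1.8). At a constant ratio, 2.0 became 1.93 at SD 0.5 and 1.78 at SD 1.0. With supply fully aligned with exposure, a true 1.0 became 0.91–1.10 or 0.84–1.19, with simulated type I error of 7–9% or 15–16%. Site-stratified Mantel-Haenszel recovered the true OR with about 95% coverage.

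**6. Setting, by diagnostic category.** Assume exposure of 60% in hospital and 30% in the community, no effect, and all 512 controls reused without adjustment. The crude OR is 1.12 for CCNA-positive cases (83 hospital, 20 community) and 0.89 for category 3 (24 and 15). For all cases pooled it is 1.02.

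**The case against.** The strongest reply concerns size. The documents give neither the between-site variance nor any link between control supply and exposure. The section 3 cohorts are not two sites of this study and may differ in population and definitions; an SD from two draws has one degree of freedom. Nothing in the documents supports an SD of 1.5. The largest distortions all need a supply–exposure association that is assumed. All of this is correct, and it limits what can be said about magnitude.

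At SD 0.5 the log bias is about ln(2.0/1.935) = 0.03 against a standard error of 0.17. The unconditional root mean squared error is then √(0.17² + 0.03²), about 0.17, no worse than the conditional standard error of 0.18–0.20. Even at SD 0.9 it is only about 0.20. The gain is clear at SD 1.5, or where supply tracks exposure.

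SAP 7.3 also fits age groups separately, where standard errors are larger (0.37–0.39 at 18–49), so the same bias harms coverage less than in the all-age simulation. Covariates such as admission source and prior healthcare contact might absorb some site variation. Setting is partly handled through item 1.4, so the complaint is complete for site but weaker for setting.

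Unconditional regression is valid if the matching factors are in the model. Here site is not, and nothing in the SAP brings it in. The size argument does not remove that mismatch.

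**Conclusion.** The concern holds and should be fixed before analysis. That the design is matched on site while the analysis ignores site is plain from SAP sections 2.1, 4, 7.2 and 7.3 and Appendix 1, and is held with high confidence. The direction follows from the design: toward 1 when control supply is unrelated to exposure, and either way when it is related.

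The size rests on assumptions. For a true odds ratio of 2.0 and unrelated supply, the shift runs from negligible (about 1.93 at SD 0.5) to material (1.65 at SD 1.5). False risk factors arise only if supply tracks exposure. Hospital versus community and the local repeat-testing policy are fixed or constrained by the matching, and cannot be ranked as patient risk factors whatever the size of the bias.

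**What to change.** - **SAP 7.3:** use conditional logistic regression stratified on participating site by hospital/community, and name the pseudonymised site code as an analysis variable. Fit each diagnostic category against all controls in its strata.
- **Age groups:** to avoid thin strata, one conditional model with age-group main effects and age-group by risk-factor terms can replace the separate fits. It assumes that age effects are common across sites.
- **Sparse subsets:** if a site random intercept is preferred, force setting in and add the site mean of each exposure. Without the site mean, simulation gave the unconditional odds ratio to within 0.01, because matching makes the case fraction nearly equal across sites. With it, the odds ratio was 2.01–2.13 for a true 2.0 (40 replicates only).
- **SAP 7.2:** report Mantel-Haenszel odds ratios on the same strata.
- **Ranking:** leave out hospital versus community and item 3.2. Finer community categories, such as GP or nursing home, may stay. Examine setting differences as risk factor by setting interactions, and treat country differences as exploratory (213/12, about 18 cases per country).

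**Cost.** This needs SAP wording and no new data collection, provided the site code is kept in the analysis file. The protocol's data protection text has the key linking code to site destroyed after data collection, so the SAP should say that the code itself is retained.

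In simulation, conditional standard errors rise 5–22% with all ages pooled (0.17 to 0.18–0.20) and about 10–31% in the 39-case category (0.34 to 0.37–0.44). In a separate 18–49 fit they rise 20–56% (0.37–0.39 to 0.46–0.59), and 12–21% of cases have no control in their stratum. The single interaction model avoids most of that (18–49 standard error 0.39–0.41, odds ratio 1.93–2.17).

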#### 3.2.2 Outcome measures

Primary outcome measure: Crude mortality at 30 days and 6 months after the sample was taken will be compared between case and controls, those that received a correct diagnosis at the original hospital and those that were 'missed' (either due to lack of testing or inadequate testing) and between community and hospitalised patients.

Secondary outcome measures: Patient length of stay, severity of infection (e.g. WCC, serum albumin, temperature), need for escalation of medical/surgical care due to gastrointestinal disease, post-infectious sequelae.

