#### 6.2. Key variables

The following is a partial list of variables that will be collected, measured and included as potential risk factors of the analysis.

- Demographic information including age, gender, etc.

- Laboratory testing for other enteric pathogens

- Medical conditions as independent variables and as a variable based on the Charleson comorbidity index (medical conditions included are listed in appendix 1)

- Medication used including antibiotics, proton pump inhibitors, drugs affecting the gastrointestinal tract, systemic steroids or immunosuppressive drugs

- Medical procedures including acute or elective surgery and GI interventions

A detailed list of the variables and definition of the variables is attached as appendix 1.

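### SAP 7.3 lets outcomes and CDI-defined items enter, and be ranked in, the risk-factor regression: 24 to 26 of the 86 Appendix 1 rows tagged for multivariate use are not pre-sample exposures

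*SAP*

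**What the plan says.** SAP 7.3 plans an unconditional logistic regression to evaluate risk factors, "with case/control as dependent variable, and all variables listed in the univariate analysis as independent variables". Variables are chosen by forward stepwise selection, and "The process of the forward selection will be recorded to rank the risk factor". There are also age-specific fits: "The regression analysis will be performed separately for the three age groups (18-49,50-64 and 65+ years").

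SAP 7.2 supplies the list. It states that "Univariate analysis will be used to assess outcomes and risk factors" and that "The variables to be included in the univariate analysis are shown in the table in appendix 1". Appendix 1 has an analysis-type column. Its outcomes block (items 10.1 to 10.7.1) carries the combined univariate and multivariate tag throughout, as do items 7.1 to 7.2.1 on escalation of CDI treatment, 4.5.1 on CDI severity, 2.7 to 2.9.1 on help and purchases during CDI, and 2.4 on discharge destination.

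Elsewhere outcomes and risk factors are kept apart. SAP 2.5 has a separate first objective, "Determine the outcomes of cases (of each classification) vs controls". Protocol 3.2.2 makes mortality an outcome: "Crude mortality at 30 days and 6 months after the sample was taken will be compared between case and controls". Protocol 3.3.6 gives its own list of risk factors. SAP 6.2 names only exposure-type variables as "included as potential risk factors of the analysis", but it describes that list as partial and refers to Appendix 1 for the full one.

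**The concern.** A risk factor must precede the event it is meant to explain. The model in 7.3 has CDI case status as its dependent variable, yet its candidate list includes things that happen after the diagnosis or that only a patient with CDI can have. Forward selection enters variables by strength of association, and consequences of CDI are associated with CDI by construction. Items such as treatment escalation should be near zero in controls negative by all assays, so they would tend to enter early.

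At stake is the risk-factor objective (objective 1.4 in the protocol, second objective in SAP 2.5). Followed as written, death, readmission or escalation could be selected and ranked as risk factors for CDI. Genuine exposures could be pushed down the ranking or lose some precision. Their odds ratios could also be biased in either direction if the consequence is linked to the exposure among cases.

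**Working it through.** **1. Row count of Appendix 1.** One numbered item, or one named co-morbidity, is one row. Rows with the combined tag, sections 1 to 10 in order (section 5 contributes only the co-morbidity block 5.7): 3 + 17 + 3 + 1 + 31 + 10 + 4 + 3 + 2 + 12 = 86. A further 34 rows are tagged univariate only, so there are 120 in all.

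**2. Rows that follow the sample or are defined through CDI.**

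| Items | Content | Rows | Main questions |
|---|---|---|---|
| 2.4 | Discharge destination | 1 | 1 |
| 2.7–2.9.1 | Help and purchases because of CDI | 6 | 3 |
| 4.5.1 | CDI severity grade | 1 | 0 |
| 6.1–6.1.1 | Antibiotics at or after the sample | 2 | 1 |
| 7.1–7.2.1 | Escalation of CDI treatment | 4 | 2 |
| 10.1–10.7.1 | Discharge, readmission, death | 12 | 7 |
| Total | | 26 | 14 |

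That is 26/86 = 30% of rows, and 14/60 = 23% of main questions (each co-morbidity counted as one question). The text of 6.1 is broken in extraction and the item mixes concurrent with later use. Without 6.1 and 6.1.1 the counts are 24 rows and 13 main questions.

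**3. Literal reading of 7.3.** Its wording takes every variable in the univariate analysis, so the 34 univariate-only rows qualify too. Eleven of them are post-sample or CDI-defined: 4.2, 4.3, 4.3.1, 4.4, 4.5, 5.11, 5.11.1 and 5.16 to 5.16.3. The total is 26 + 11 = 37 of 120, or 35 without 6.1 and 6.1.1. It is higher if straddling rows count, such as 5.10, which records diarrhoea on both sides of the sample.

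**4. Is the analysis-type column a filter?** Using it keeps all 24 to 26 rows. It also drops contact with a CDI case (5.13), kissing contact with an infant (5.14) and previous CDI (4.6), all listed as risk factors in protocol 3.3.6. It errs in both directions.

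**5. Illustrative size.** From the SAP: 213 cases and 512 controls (Table 1), previous surgery 26% v 16% and antibiotics 67% v 45% (section 3). The surgery odds ratio is (0.26 × 0.84)/(0.16 × 0.74) = 1.84; its power alone is about 86% pooled. Assumed: the rates of an escalation item and a death item, no link between them and surgery, and age groups holding a third (71 v 171) or a quarter (53 v 128) of patients. Forward selection at 5% used four candidates: surgery, antibiotics, escalation and death.

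| Assumed escalation; death (cases v controls) | At least one post-sample item selected: pooled / third / quarter |
|---|---|
| 10% v 0.5%; 20% v 8% | 100 / 98 / 94% |
| 5% v 0.5%; 12% v 8% | about 98 / 67 / 58% |
| 3% v 0.5%; 10% v 8% | about 73–76 / 39 / 30–34% |

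If both items were unrelated to case status, chance selection would be about 1 − 0.95² = 10%.

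Ranking needs two separate counts. As a share of all runs, both surgery and a post-sample item enter, with the post-sample item first, in about 26% to 80% of pooled runs and about 4% to 34% at third or quarter size. Runs in which surgery never enters are a different matter. At third or quarter size surgery has only about 44% or 33% power by itself, so most of those runs would lose surgery anyway.

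**6. Effect on the surgery odds ratio.** Against 1.84, a 10% v 0.5% escalation item linked to surgery by −5 to +10 percentage points gives 1.94 to 1.67. A 20% v 8% death item linked by −10 to +10 points gives 1.93 to 1.77.

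**The case against.** The best defence is intent. Section 7.3 opens by saying that it evaluates risk factors, Appendix 1 labels section 10 as outcomes and has a time-window column, and SAP 6.2 names no outcome or CDI treatment item. Few analysts would interpret CDI-linked death as a risk factor. The section 10 tags may have been meant for models with an outcome as dependent variable. All of this makes a drafting oversight likely. It does not supply a rule: 6.2 is a partial list that defers to Appendix 1, no outcome regression is specified, and a pre-specified plan should not depend on the analyst overriding its own sentence.

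Two stronger readings are tempting and are not supported. A reader might infer that the sponsor means to treat death as a cause of CDI; SAP 2.5 and protocol 3.2.2 and 3.3.6 point the other way. A reader might also infer that post-sample items would displace real risk factors in about 90% of age-group models. Under the strongest assumed rates a figure near that arises only by adding runs where surgery does not enter: at quarter size, about 21% with both entering and 68% without surgery. Most of the second part is low power, not displacement.

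It is also fair that the simulation shows mechanism rather than size. The consequence rates and age shares are assumed, four candidates stand in for 60 to 120, and Table 1 gives the maximum that could be recruited.

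**Conclusion.** Wrong as written. The counts rest on the documents alone: 24 to 26 of 86 rows tagged multivariate (13 to 14 of 60 main questions), and at least 35 to 37 of 120 on the literal wording, are not pre-sample exposures, and nothing in the SAP excludes them from the candidate list.

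The practical size is less certain. Under the assumed rates, selection of at least one such item is likely in the pooled data and well above chance in smaller groups. Bias in the odds ratios of true exposures from modest items is small. The main consequence is an invalid list and ranking of risk factors, in the only multivariable analysis of a main objective.

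**What to change.** 1. State in 7.3 that candidates are exposures and background variables dated before the index sample. Add a column to Appendix 1 marking each row as risk factor or outcome/descriptive.
2. Take 2.4, 2.7–2.9.1, 4.2–4.5, 4.5.1, 5.11–5.11.1, 5.16–5.16.3, all of section 7 and all of section 10 out of the candidate list. Analyse them as outcomes or descriptively.
3. Keep 6.1–6.1.1 out unless start dates separate courses begun before the sample. Item 6.2 already covers the preceding 12 weeks.
4. Apply the same date rule to every row that can straddle the sample: 2.2–2.2.1, 3.1–3.1.1, 5.1–5.4, 5.10, 5.12, 5.15, cardiac arrest and its date, renal replacement and the acute co-morbidities.
5. Make 5.13 and 5.14 candidates, in line with protocol 3.3.6.
6. Do not simply re-tag previous CDI (4.6). As worded it can count the index episode, and SAP 4.1.5 removes controls, but not cases, with a CDI-positive sample within 8 weeks either side. Use it only if restricted to episodes before the sample and with the 8-week window handled alike in both groups, for example by counting only episodes more than 8 weeks earlier. Otherwise report it descriptively.

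The cost is SAP wording, re-tagging and a date check; no new data are needed. Of the 86 tagged rows, 86 − 26 = 60 remain. Seven of those (2.2, 2.2.1, 3.1, 3.1.1, cardiac arrest, its date, renal replacement) need the check, plus any acute conditions among the 22 co-morbidity rows without a window of their own. The downside is a shorter candidate list. Setting-specific models and analyses with and without undated rows are optional and separate from this error.
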